## 5.3. Handling and Storage of Study Treatment

Eltrombopag tablets and PfOS sachets must be stored in a secure area under the appropriate physical conditions for the product according to the requirements listed on the label. Access to and administration of the study treatment will be limited to the investigator and authorized site staff. Study treatment must be dispensed or administered only to subjects enrolled in the study and in accordance with the protocol.

Eltrombopag tablets and PfOS sachets will be stored at a controlled room temperature of 20-25°C (68-77°F); excursions between 15-30°C (59-86°F) are permissible.

## 5.4. Treatment Assignment

Subjects will be identified by a unique subject number that will remain consistent for the duration of the study.

Upon completion of all the required screening assessments, eligible subjects will be registered into the trial by the investigator or authorized site staff. All enrolled subjects will receive eltrombopag (tablets or PfOS).

## 5.5. Blinding

This is an open-labeled study.

## 5.6. Product Accountability

In accordance with local regulatory requirements, the investigator, designated site staff, or head of the medical institution (where applicable) must document the amount of investigational product dispensed and/or administered to study subjects, the amount returned by study subjects, and the amount received from and returned to GSK, when applicable. Product accountability records must be maintained throughout the course of the study. Refer to the SPM for further detailed instructions on product accountability.

## 5.7. Treatment Compliance

At each visit, an evaluation of subject compliance with taken medication will be performed.

Compliance with eltrombopag will be assessed through querying the subject during the site visits and documented in the source documents and IP dispensing log.

A record of the number of eltrombopag tablets or sachets dispensed to and taken by each subject must be maintained and reconciled with study treatment and compliance records. Treatment start and stop dates, including dates for treatment delays and/or dose reductions will also be recorded in the IP dispensing log.

The investigator will make every effort to bring non-compliant subjects into compliance. If in the opinion of the investigator, there are any significant irregularities in compliance, and the subject cannot be brought back into compliance, then the subject should be withdrawn from the study.

# 5.8. Monitoring, Interruption and Stopping Criteria for Hepatobiliary Events

### 5.8.1. Liver chemistry stopping criteria

Liver chemistry stopping criteria and follow up requirements have been designed to assure subject safety and evaluate liver event etiology in alignment with the FDA Guidance for Industry – Drug-Induced Liver Injury: Premarketing Clinical Evaluation (July 2009, www.fda.gov).

#### Liver chemistry stopping criteria 1-5 are defined as follows:

1. ALT  $\ge 3x$  ULN and bilirubin  $\ge 2x$  ULN (>35% direct bilirubin) (or ALT  $\ge 3x$  ULN and INR > 1.5, if INR measured)

**NOTE:** If serum bilirubin fractionation is not immediately available, study drug should be discontinued if  $ALT \ge 3x$  ULN **and** bilirubin  $\ge 2x$  ULN. Serum bilirubin fractionation should be performed if testing is available. If testing is unavailable, **record presence of detectable urinary bilirubin on dipstick**, indicating direct bilirubin elevations and suggesting liver injury.

- 2. ALT > 5x ULN
- 3. ALT  $\geq$  3x ULN if associated with symptoms (new or worsening) believed to be related to hepatitis (such as fatigue, nausea, vomiting, right upper quadrant pain or tenderness, or jaundice) or believed to be related to hypersensitivity (such as fever, rash or eosinophilia).
- 4. ALT > 3x ULN persists for > 4 weeks
- 5. ALT  $\geq$  3x ULN and cannot be monitored weekly for 4 weeks

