# 4.2. Permanent Discontinuation from Study Treatment and Subject Completion Criteria

## 4.2.1. Permanent Discontinuation from Study Treatment

Study treatment must be permanently discontinued for any of the following reasons:

- The subject is pregnant.
- The subject is significantly non-compliant with the requirements of the protocol.
- The subject has an adverse experience that would, in the investigator's judgment, make continued participation in the study an unacceptable risk.
- The subject has a thrombotic event, unless in the opinion of the investigator interruption of eltrombopag would lead to a risk of bleeding that would outweigh the risk of thrombosis.
- The subject meets stopping criteria for liver chemistry defined in Section 5.8.1.
- At the request of the subject or proxy

In addition study treatment may be permanently discontinued for any of the following reasons:

TRA117366

- Due to deviation(s) from the protocol
- At the investigator's discretion
- The subject is lost to follow-up
- The study is closed or terminated.

Study treatment will be discontinued within 3 months for the following reasons, and subject will be considered to have completed the study per Section 4.2.2:

- The subject reaches 18 years of age.
- The subject is in treatment phase when local regulatory approval is received for eltrombopag for the treatment of pediatric chronic ITP.

The primary reason study treatment was permanently discontinued must be documented in the subject's medical records and CRF.

If the subject (or guardian) withdrawals consent, the Investigator must document the reason for withdrawal of consent in the CRF if specified by the subject or guardian.

If the subject voluntarily discontinues from treatment due to toxicity, 'adverse event' will be recorded as the primary reason for permanently discontinuation on the CRF rather than subject decision.

Once a subject has been permanently discontinued from study treatment, retreatment with study treatment will not be allowed.

All subjects who discontinue from study treatment will have safety assessments at the time of discontinuation and will have follow-up visits at 1, 2, 3, and 4 weeks after the final dose of study treatment, as specified in Time and Events Table, Table 3.

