### When any of the liver chemistry stopping criteria 1 - 5 is met, do the following:

- Immediately discontinue study treatment
- Report the event to GSK within 24 hours of learning its occurrence
- Complete the liver event CRF and SAE data collection tool if the event also meets the criteria for an SAE
  - All events of ALT ≥ 3x ULN and bilirubin ≥ 2x ULN (>35% direct bilirubin) (or ALT ≥3x ULN and INR > 1.5, if INR measured; INR measurement is not required and the threshold value stated will not apply to subjects receiving anticoagulants), termed 'Hy's Law', must be reported as an SAE (excluding studies of hepatic impairment or cirrhosis).
  - NOTE: if serum bilirubin fractionation is not immediately available, study treatment should be discontinued if ALT ≥ 3x ULN and bilirubin ≥ 2x ULN. Serum bilirubin fractionation should be performed if testing is available. If testing is unavailable, record presence of detectable urinary bilirubin on dipstick, indicating direct bilirubin elevations and suggesting liver injury.
- Complete the liver imaging and/or liver biopsy CRFs if these tests are performed
- Perform liver event follow up assessments, and monitor the subject until liver chemistries resolve, stabilize, or return to baseline values as described below
- Do not rechallenge with investigational product.

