## 5.8.1.2. Liver Chemistry Monitoring Criteria

For subjects with ALT  $\ge 3x$  ULN **but** < 5x ULN **and** bilirubin < 2x ULN, without hepatitis symptoms or rash, and who can be monitored weekly for 4 weeks, the following actions should be taken:

- Notify the GSK Medical Monitor within 24 hours of learning of the abnormality to discuss subject safety
- Can continue study treatment
- Must return weekly for repeat liver chemistries (ALT, AST, alkaline phosphatase, bilirubin) until they resolve, stabilize or return to within baseline values
- If at any time the subject meets any of the liver chemistry stopping criteria 1-5, proceed as described above
- If, after 4 weeks of monitoring, ALT <3x ULN and bilirubin <2x ULN, monitor subjects twice monthly until liver chemistries normalize or return to within baseline values.

Refer to Appendix 1 for algorithm of liver chemistry monitoring, stopping and follow up criteria.

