# g. Protocol-Specific SAEs

• All events of possible drug-induced liver injury with hyperbilirubinaemia defined as ALT ≥ 3xULN and bilirubin ≥ 2xULN (>35% direct) (or ALT ≥ 3xULN and INR>1.5, if INR measured) or termed 'Hy's Law' events (INR measurement is not required and the threshold value stated will not apply to patients receiving anticoagulants).

NOTE: bilirubin fractionation is performed if testing is available. If testing is unavailable, record presence of detectable urinary bilirubin on dipstick indicating direct bilirubin elevations and suggesting liver injury. If testing is unavailable and a subject meets the criterion of total bilirubin  $\geq 2xULN$ , then the event is still reported as an SAE. If INR is obtained, include values on the SAE form. INR elevations >1.5 suggest severe liver injury

- All Grade 4 laboratory abnormalities assessed using the National Cancer Institute (NCI) Common Terminology Criteria for Adverse Events (CTCAE) (see The Study Procedures Manual for: Common Terminology Criteria for Adverse Events), except Grade 4 thrombocytopenia.
- An ocular event of clinical concern as defined in Section 7.2.1.4.1 Ocular Changes of Clinical Concern.

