#### 7.2.2.6. Prompt Reporting of SAEs and Other Events to GSK

SAEs, pregnancies, and liver function abnormalities meeting pre-defined criteria will be reported promptly by the investigator to GSK as described in the following table once the investigator determines the event meets the protocol definition for that event.

	Initial Reports	Reports Follow-up Information on a Previous Report		
Type of Event	Time Frame	Documents	Time Frame	Documents
All SAEs	24 hours	SAE data collection tool	24 hours	Updated SAE data collection tool
Pregnancy	2 Weeks	Pregnancy Notification Form	2 Weeks	Pregnancy Follow up Form
Liver chemistry abnorn	nalities:			
ALT≥3xULN and bilirubin≥1.5xULN (>35% direct) (or ALT≥3xULN and INR>1.5, if INR measured)³	24 hours 	SAE data collection tool. Liver Event Case Report Form (CRF) and liver imaging and/or biopsy CRFs if applicable 	24 hours	Updated SAE data collection tool. Updated Liver Event CRF 
ALT≥5xULN; ALT≥3xULN with hepatitis or rash or ALT ≥3xULN and <5xULN that persists ≥4 weeks	24 hours 	Liver Event CRF 	24 hours	Updated Liver Event CRF 
ALT≥3xULN and <5xULN and biliribin <1.5xULN	24 hours 	Liver Event CRF does not need completing unless elevations persist for 4 weeks or subject cannot be monitored weekly for 4 weeks 		

- 1. GSK to be notified at onset of liver chemistry elevations to discuss subject safety.
- 2. Liver event documents should be completed as soon as possible
- 3. INR measurement is not required; if measured, the threshold value stated will not apply to subjects receiving anticoagulants.

Methods for detecting, recording, evaluating, and following up on AEs and SAEs plus procedures for completing and transmitting SAE reports to GSK are provided in the SPM. Procedures for post-study AEs/SAEs are provided in the SPM.

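### Liver stopping criterion 1 applies its INR limb without an anticoagulant exception, the SAE and reporting text for the same limb has one, and the protocol does not say whether it extends to stopping

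*Protocol*

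**What the plan says.** **The stopping rule.** Protocol Section 5.8.1, criterion 1, has two limbs. Both need ALT at least 3x ULN. One adds bilirubin at least 2x ULN with more than 35% direct. The other is ALT at least 3x "ULN and INR > 1.5, if INR measured". Neither limb mentions anticoagulants.

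**The exception.** The ALT/INR limb is restated in three places, each with an exception:

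- Section 5.8.1, list of actions once a criterion is met, in the sub-bullet on which events must be reported as an SAE: "INR measurement is not required and the threshold value stated will not apply to subjects receiving anticoagulants".
- Section 7.2.2.2, item g, protocol-specific SAEs: "INR measurement is not required and the threshold value stated will not apply to patients receiving anticoagulants".
- Section 7.2.2.6, footnote 3 to the prompt-reporting table: "if measured, the threshold value stated will not apply to subjects receiving anticoagulants".

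**The consequences.** Section 4.2.1 lists this among the reasons for mandatory permanent discontinuation: "The subject meets stopping criteria for liver chemistry defined in Section 5.8.1". The Section 5.8.1 action list adds: "Do not rechallenge with investigational product".

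**The alternative pathway.** Section 5.8.1.2 lets treatment continue under weekly liver tests when ALT is at least 3x but below 5x ULN and bilirubin is below 2x ULN, in subjects "without hepatitis symptoms or rash, and who can be monitored weekly for 4 weeks". It has no INR condition, and it gives way whenever any of criteria 1 to 5 is met.

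**The concern.** The protocol states three times that an INR limit of 1.5 is not to be used in a subject on anticoagulants. It then uses the same limit, unqualified, in the one place where the result is an irreversible stop. For a child whose ALT is raised but within the monitoring range, the INR value decides between weekly monitoring and permanent discontinuation. If that INR reflects an anticoagulant, a stop recorded as a liver event may not be one.

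Sites have little room to resolve this themselves, because Section 3 bars waivers or exemptions except for immediate safety concerns.

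The results would be affected as follows. Section 7.2.2.3 requires an associated AE for any laboratory result that leads to permanent discontinuation. Such an AE counts in the frequency of all AEs, which SAP Section 1.2 makes the primary endpoint, and it can enter the SAP Section 2.6.1 table of AEs leading to discontinuation. The patient's exposure would also be cut short.

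**Working it through.** The plan gives no figure to reproduce, so the check is a comparison of texts followed by an enumeration of the rule.

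**1. Passages side by side**

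| Place | Purpose | INR limb | Bilirubin limb | Anticoagulant exception |
|---|---|---|---|---|
| 5.8.1, criterion 1 | Stop treatment | ALT ≥3x ULN and INR >1.5 if measured | ≥2x ULN, >35% direct | No |
| 5.8.1, action list | SAE reporting | Same | Same | Yes |
| 7.2.2.2, item g | SAE definition | Same | Same | Yes |
| 7.2.2.6, table and footnote 3 | Reporting timelines | Same | ≥1.5x ULN, >35% direct | Yes |

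The Section 7.2.2.6 row matches criterion 1 on the ALT/INR limb only, because its bilirubin limit is different.

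**2. Where the exception would change the stop decision**

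An illustrative grid (the values are assumptions, chosen to straddle each threshold):

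- ALT: 1, 2.9, 3, 4, 5 and 5.1 times ULN (6 values)
- Bilirubin: 1, 1.9, 2 and 3 times ULN (4 values)
- INR: not measured, 1.2, 1.6 and 2.5 (4 values)
- Anticoagulant: no, yes (2 values)

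Cells: 6 × 4 × 4 × 2 = 192.

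Rule as written: stop if (ALT ≥3x and bilirubin ≥2x), or (ALT ≥3x and measured INR >1.5), or ALT >5x (criterion 2). Rule with the exception carried over: the same, except that the INR limb is ignored in anticoagulated subjects. Criteria 3 to 5 are taken as not met, and bilirubin ≥2x is taken as satisfying the bilirubin limb.

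The two rules differ in 12 of the 192 cells: 3 ALT values (3, 4, 5) × 2 bilirubin values (1, 1.9) × 2 INR values (1.6, 2.5) × 1 (anticoagulated) = 12. All 12 have ALT from 3x to 5x ULN, bilirubin below 2x ULN and measured INR above 1.5.

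In 2 × 2 × 2 = 8 of these cells ALT is below 5x ULN. There the Section 5.8.1.2 pathway would apply if the INR limb did not, provided its conditions on symptoms and weekly monitoring are met. The other 4 have ALT at exactly 5x ULN, which meets neither criterion 2 (above 5x) nor the monitoring range (below 5x).

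These counts describe the grid. They are not expected frequencies.

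**3. How a case could arise**

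INR is not in the current Time and Events Table (Table 3) or the list of local laboratory tests (Table 4), so the limb can operate only when INR is measured for another reason. The exclusion criteria (4.1.3) and prohibited medications (6.2) do not name anticoagulants. Section 4.2.1 requires discontinuation after thrombosis with a qualification: "The subject has a thrombotic event, unless in the opinion of the investigator interruption of eltrombopag would lead to a risk of bleeding", where that risk is judged to outweigh the thrombotic one. A subject could therefore remain on treatment after a thrombotic event. The documents do not say how such an event would be treated.

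**4. Scale**

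One patient out of a maximum of 12 is 1/12 = 8.3%. This is the weight of a single case, not an estimate of how often it would occur.

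**The case against.** **Different scope is not contradiction.** The three exceptions concern what is an SAE and how it is reported; criterion 1 concerns stopping. A stopping rule may be wider than an SAE definition, and criteria 2 to 5 already stop treatment without being Hy's Law events. This stands, and the stricter rule may be deliberate. But no passage says so, and the text gives no reason why the limit is unsuitable for classifying an event yet suitable for ending treatment.

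**The nearby text may already qualify the rule.** The first exception lies in the same section, just below criterion 1, and a site could read it as covering the section's only INR threshold. That is possible, but it means two sites could treat the same child differently.

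**Misattribution would be visible.** Section 5.8.1.1 requires recording of concomitant medication and an aetiology work-up. SAP Sections 2.4.2, 2.6.3 and 2.6.4.1 list medications, laboratory data and liver events. With so few patients, a reader could see the anticoagulant beside the stop. This stands for interpretation, but it does not undo the stop.

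**Stronger readings that the documents do not support.**

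- *One passage orders a stop and another orders continued treatment.* The action list in 5.8.1 begins with immediate discontinuation, and 5.8.1.2 yields to criteria 1 to 5. Once criterion 1 is met, every passage leads to a stop. The open question is whether the INR limb should count towards meeting it.
- *An anticoagulant effect alone forces a stop.* ALT must also be at least 3x ULN, and INR counts only if measured.
- *The limb would operate mainly in anticoagulated children.* This is conjecture. Section 7.2.2.2 treats a raised INR as a sign of severe liver injury, so testing during the work-up of a raised ALT is an equally plausible reason to have a value.

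**Conclusion.** The mismatch is real but narrow. As the text stands, an anticoagulated subject with ALT at least 3x and below 5x ULN, bilirubin below 2x ULN, no hepatitis symptoms or rash, weekly monitoring possible and a measured INR above 1.5 must stop permanently. The protocol's own SAE text says that the INR threshold does not apply to that subject.

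It is a minor point for the trial as a whole. The analysis is descriptive, with no hypothesis test, and the case needs several conditions at once. For a patient who met them, the consequence would be irreversible.

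The conclusion rests on the body text being read literally and on anticoagulated subjects being able to remain on treatment, which the documents do not exclude. One part cannot be checked: the Appendix 1 liver algorithm is not shown, and it may carry the exception.

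**What to change.** Reconcile the INR condition in criterion 1 of Section 5.8.1, and in the Appendix 1 algorithm, with the Section 5.8.1 action list, Section 7.2.2.2 item g and footnote 3 of Section 7.2.2.6. State explicitly whether the anticoagulant exception applies to stopping as well as to reporting. If the difference is intended, one sentence saying so is enough. Which rule applies is a clinical decision for the sponsor.

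The cost is one phrase in the protocol and a check of the algorithm. It needs no new data, visit or staff, and no change to the SAP.

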### When any of the liver chemistry stopping criteria 1 - 5 is met, do the following:

- Immediately discontinue study treatment
- Report the event to GSK within 24 hours of learning its occurrence
- Complete the liver event CRF and SAE data collection tool if the event also meets the criteria for an SAE
  - All events of ALT ≥ 3x ULN and bilirubin ≥ 2x ULN (>35% direct bilirubin) (or ALT ≥3x ULN and INR > 1.5, if INR measured; INR measurement is not required and the threshold value stated will not apply to subjects receiving anticoagulants), termed 'Hy's Law', must be reported as an SAE (excluding studies of hepatic impairment or cirrhosis).
  - NOTE: if serum bilirubin fractionation is not immediately available, study treatment should be discontinued if ALT ≥ 3x ULN and bilirubin ≥ 2x ULN. Serum bilirubin fractionation should be performed if testing is available. If testing is unavailable, record presence of detectable urinary bilirubin on dipstick, indicating direct bilirubin elevations and suggesting liver injury.
- Complete the liver imaging and/or liver biopsy CRFs if these tests are performed
- Perform liver event follow up assessments, and monitor the subject until liver chemistries resolve, stabilize, or return to baseline values as described below
- Do not rechallenge with investigational product.

#### In addition, for subjects meeting liver stopping criterion 1:

- Make every reasonable attempt to have subjects return to clinic within 24 hours for repeat liver chemistries, liver event follow up assessments (refer to Section 5.8.1.1), and close monitoring
- A specialist or hepatology consultation is recommended
- Monitor subjects twice weekly until liver chemistries (ALT, AST, alkaline phosphatase, bilirubin) resolve, stabilize or return to within baseline values.

#### For subjects meeting any of the criteria 2-5:

- Make every reasonable attempt to have subjects return to clinic **within 24-72 hrs** for repeat liver chemistries and liver event follow up assessments (refer to Section 5.8.1.1)
- Monitor subjects weekly until liver chemistries (ALT, AST, alkaline phosphatase, bilirubin) resolve, stabilize or return to within baseline values;
  - subjects meeting criterion 5 should be monitored as frequently as possible.

#### 5.8.1.1. Liver Event Follow Up Assessments

For subjects meeting any of the liver chemistry stopping criteria 1-5, make every attempt to carry out the **liver event follow up assessments** described below:

- Viral hepatitis serology including:
  - Hepatitis A IgM antibody
  - Hepatitis B surface antigen and Hepatitis B Core Antibody (IgM)
  - Hepatitis C RNA
  - Cytomegalovirus IgM antibody
  - Epstein-Barr viral capsid antigen IgM antibody (or if unavailable, obtain heterophile antibody or monospot testing)
  - Hepatitis E IgM antibody
- Serum creatine phosphokinase (CPK) and lactate dehydrogenase (LDH).
- Fractionate bilirubin, if total bilirubin  $\geq 2x$  ULN.
- Obtain complete blood count with differential to assess eosinophilia.
- Record the appearance or worsening of clinical symptoms of hepatitis, or hypersensitivity, such as fatigue, nausea, vomiting, right upper quadrant pain or tenderness, fever, rash or eosinophilia as relevant on the AE form.
- Record use of concomitant medications, acetaminophen, herbal remedies, other over the counter medications, or putative hepatotoxins, on the concomitant medications form.

Record alcohol use on the liver event alcohol intake form.

The following assessments are required for subjects with ALT  $\ge 3x$  ULN and bilirubin  $\ge 2x$  ULN (>35% direct) but are optional for other abnormal liver chemistries:

- Anti-nuclear antibody, anti-smooth muscle antibody, and Type 1 anti-liver kidney microsomal antibodies
- Liver imaging (ultrasound, magnetic resonance, or computerized tomography) to evaluate liver disease.

